• Fecal matter samples collected at home at intake, week 4, week 8 and at week 10 will be sent to our collaborator [name] at Northeastern University

• All females who are post-menarche and pre-menopausal will be required to take a urine pregnancy test at the time of the intake (Test performed at Quest Diagnostic)

• Storage for biorepository for analysis at the end of the study. This will include Blood (serum, plasma, whole blood) and urine collected at baseline and week 10). (More information is provided in the blood and other biological samples subsection)

The results of laboratory tests done through Quest will be accessible to the study clinicians via a HIPPA compliant, secure EHR portal provided by Quest Diagnostics.

While some of these samples will be sent to known collaborators, others will be stored in anticipation of future collaborations. The known collaborators for stored samples include samples to: a) the Center for Applied Proteomics at George Mason University; b) [name] at Columbia for inflammatory and immune markers; c) [name] at Columbia for coinfection markers; and d) Drs. [name] (University of Missouri) and [name] at (UCSD) for lipidomic markers.

All Participants (Remote, Hybrid and In-Person) will also complete the following as part of study visits:

Medical history and psychiatric diagnostic Interview MINI

At intake, all subjects will undergo structured diagnostic interviews in-person or via telehealth, which include questions about their current and psychiatric history using MINI. A medical history will be obtained at intake using the Self-Administered Comorbidity Questionnaire (SCQ) and by the study clinician during the clinician interview.

Self-report questionnaires

Participants will have in-person or telehealth assessments at baseline and at weeks 1, 2, 4, 6, 8, 10. Participants will complete self-report questionnaires every 2 weeks at each assessment throughout the study and at Week 14.

These self-report questionnaires and research data will be collected electronically via REDCap (Research Electronic Data Capture), hosted by New York State Psychiatric Institute. REDCap is a secure web application for building and managing online surveys and databases that complies with HIPAA requirements for a secure database.

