For in-person participants who opt to complete paper versions of the questionnaires, this data will be stored in locked files and will be kept confidential to the extent permitted by law. Research binders will be available only to research staff and Federal, State and Institutional personnel as part of routine audits. Paper versions of self-report questionnaires will be labeled with a research number assigned to the patient, not the patient's name.

Wearing of activity monitor

All participants will be provided with an activity monitor (e.g., Fitbit) to keep track of sleep and of the number of steps taken each day. Participants will wear this device for 2 weeks prior to randomization and throughout the 14 weeks of the study. We will also inform the participants that they will need to share the data from their devices periodically during their study visits.

Phone-calls at end of Weeks 3, 5,7, 9 and 12 (10-20 mins)

The follow-up phone calls will be done by one of the study clinicians and will focus on inquiring about the following-

- If the participant is experiencing side-effects related to disulfiram
- If the participant is adhering to the study treatment
- If the participant has used any kind of substance like alcohol, cannabis etc.
- If the participant has started any new medications

Treatment Phase

Patients will be randomly assigned to one of two groups.

Both groups (the 4 week duration and the 8 week duration groups) will share the same protocol for the first 4 weeks as follows:

- Week 1 Disulfiram 250 every other day
- Week 2 Disulfiram 250 daily.
- Week 3 Disulfiram 250 alternating with 500
- Week 4 Disulfiram 500 daily.

Week 5-8 Continue with 500 daily (2 pills daily of disulfiram or placebo) or lower if needed based on side effects. (Note: the last 4 weeks of the study are double-blind)

(The long duration group will increase to two pills daily (500 mg) or the highest dosing regimen they can tolerate without significant side effects, while the short duration group during the last 4 weeks of the treatment period will be given placebo pills).

In-person patients will be seen in the clinic at least every 2 weeks to week 10 and at week -14 for a followup. Remote and Hybrid patients will be seen in via scheduled telehealth sessions at least every 2 weeks up to week 10 and at week -14 for follow-up. Additionally, when not seen in person or via telehealth, patients will be followed up weekly over the phone to week 12.

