Should a patient need to be discontinued from the study before week 10, he/she will be asked to return to NYSPI or to complete a telehealth evaluation and an assessment with their local physician (if participating remotely) to complete the major week 8/10 assessments so that his/her progress can continued to be evaluated by the study clinician. Since we do not know the optimal duration of disulfiram (ie, shorter courses may be effective) and because improvement may occur during the weeks after discontinuation, we will ask patients to return at week 10 (or to complete telehealth and local evaluations) but also to complete self-reports assessments and telephone follow-up at home at weeks 2, 6, 8, and 14.

Should a patient who drops from treatment early plan to start a new treatment that might impact clinical ratings, we will ask the patient to complete the full set of week 10 assessments early so that these can be used in the final data analysis; that patient will then be discontinued from both the treatment and assessment phase of the study. The patient will also be asked to return all study medication which we will then return to the NYSPI pharmacy.

During COVID-19 pandemic: I attest to follow the COVID-19 Safety Guidelines for Columbia Psychiatry and NYSPI Re-Entry outlined in the NYSPI Director's June 1st memo, which include but are not limited to:

• Infection Control/PPE – Guidelines

• Research participants will only come on-site if absolutely necessary for study procedures.

• No volunteers/externs on-site during Stage 1.

• Clinical research teams will screen their participants for COVID symptoms (night before and day of onsite visit, documenting this in the chart), and escort them in and out of the building.

• COVID/COVID-like symptoms in participants will be reported to the IRB via PRISM as an SAE.

You can upload charts or diagrams if any

Criteria for Early Discontinuation

Criteria for Early Discontinuation

Patients will be monitored for global clinical change (CGI Change - clinician rating) and for side-effects of the medications (Saftee) during the clinic visits or telehealth visits and weekly phone check-ups.

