Study Objectives	A study is a preliminary investigation regarding the relative benefit of 4 vs 8 weeks of treatment with disulfiram. With this initial study, the investigators will be able to evaluate the side effects, tolerability and initial signs of the effectiveness of disulfiram in reducing symptoms among the 24 patients assessed. The results of this study will guide the investigators regarding whether a larger definitive randomized trial should be conducted, and which treatment schedule is optimal.
Primary endpoint	Week 10 evaluation.
Study Design	A small 14-week randomized placebo-controlled pilot study enrolling 24 patients with persistent symptoms despite prior antibiotic treatment for Lyme disease (known as Post-treatment Lyme Disease Syndrome). Among the 24 disulfiram-treated patients, half will get 8 weeks of disulfiram and the other half will get a shorter duration of disulfiram for 4 weeks followed by 4 weeks of matching placebo. After week 8, patients will be off pills for 2 weeks for the primary week 10 evaluation and then for another 4 weeks for the week 14 follow-up evaluation. This will be a double-blinded study; neither physician nor patient will know which treatment group the patient is assigned to. For details see PSF.
General Study Population	See PSF respective section
Inclusion- Exclusion Criteria	See PSF respective section
Study Assessments	See PSF respective section
Sample size	24 as of 04/02/2019. The study was terminated in 2022 with a sample size of 11.
Randomization	This will be a double-blinded study; neither physician nor patient will know which treatment group the patient is assigned to. Randomization is performed at New York Psychiatric Institute pharmacy when medication is issued to an enrolled participant. Randomization is performed in blocked of 12. The study unblind will occur when the enrollment is completed, and all patients finish their follow-up assessments.
Primary aim#1	To assess the safety and side effect profile of disulfiram among patients with post treatment Lyme symptoms. This will be assessed by SAFTEE (systematically) as well as recording all unanticipated adverse events/serious adverse events.
Primary aim #2	To investigate whether treatment with disulfiram results in a meaningful reduction in fatigue and improvement in the quality of life among patients

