Analysis Analysis Population Missing Data Interim Analyses and Data	The rationale for the Fitbit is that our primary outcome is fatigue. People who are less fatigued may be engaging in more activity, such as doing more steps during the day. Moreover, activity monitoring using a device such as a Fitbit is being increasingly used in research studies as a measure of the change in response to treatment. Analysis will be performed after the study is unblinded. We conduct intent to treat analysis which covers all enrolled patients who received a study drug and who participated in at least one post-baseline assessment. Missing data is treated as missing at random

Primary aim#1 analysis	Tables on all mortality rate, SAE and AE will be generated. To estimate safety, number of adverse events in active and sham treatment groups by the end of 10-week period will be computed and reported.
Primary aim#2 analysis	To investigate whether treatment with disulfiram results in a meaningful reduction in fatigue and improvement in the quality of life, a change in scores between the baseline and week 10 will be computed. We will calculate a number of participants who's change in score reached a minimal clinically significant difference (MCID) for each of the measures. MCID for Fatigue Severity Scale (FSS) and MCID for Quality-of-Life Enjoyment and Satisfaction Questionnaire (Q-LES-Q) is 6.8. A Log Odds ratio for 8-week and 4-week group will be computed along with the 95% confidence interval for this ratio. The 95% confidence interval provides considerably more information than testing a specific null hypothesis: it provides a range of plausible values for differences in these primary outcomes between treatment groups which can be used to inform research in larger studies.

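### The only stated estimate for the primary safety aim is a number of adverse events per group, with no count of participants affected, no repeat-report rule and no interval

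*Combined protocol and SAP*

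**What the plan says.** The SAP row for the primary aim 1 analysis has two sentences. The first promises tables: "Tables on all mortality rate, SAE and AE will be generated". It does not say whether these count events or participants. The second gives the estimate: "number of adverse events in active and sham treatment groups by the end of 10-week period will be computed and reported". No denominator, confidence interval, observation time or rule for repeated reports is stated there or elsewhere.

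On data collection, the SAP row for primary aim 1 says: "This will be assessed by SAFTEE (systematically) as well as recording all unanticipated adverse events/serious adverse events". The protocol's Criteria for Early Discontinuation section says patients are monitored "for side-effects of the medications (Saftee) during the clinic visits or telehealth visits and weekly phone check-ups". The Self-report questionnaires section schedules "assessments at baseline and at weeks 1, 2, 4, 6, 8, 10", and Study Procedures adds clinician calls at the end of weeks 3, 5, 7, 9 and 12, with side effects as the first listed question.

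For participants who stop early, the protocol asks for a return at week 10 and also that they "complete self-reports assessments and telephone follow-up at home at weeks 2, 6, 8, and 14". Those who plan a new treatment that could affect ratings complete the week 10 set early and then leave assessment. The Treatment Phase section, however, keeps weekly telephone follow-up to week 12 for weeks without a visit and makes no exception for people off treatment.

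**The concern.** Safety is one of two primary aims, and the results are meant to guide whether a definitive trial follows and which schedule it uses. The question for that decision is how many people were harmed, in what way and how badly. An event total mixes three things: how many people had a problem, how long it lasted, and how often they were asked.

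That mixture matters here for three reasons. Contacts are frequent. The protocol's own comment on a published clinic series says that several complaints typical of the drug are also frequent in the underlying condition, so persistent reports are to be expected. And the progress report says that stopping because of adverse events exceeded expectation, so any thinner follow-up after stopping falls on people already affected.

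The next SAP row treats efficacy differently. It counts participants who reach a threshold, and it argues for a 95% confidence interval because an interval is more informative at this size. The safety aim gets neither.

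**Working it through.** The plan states no safety rate or sample-size figure, so there is nothing of its own to reproduce. The checks below use its schedule and sample size.

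**1. Contacts by week 10.** Visits at weeks 1, 2, 4, 6, 8, 10 = 6. Calls at weeks 3, 5, 7, 9 = 4 (week 12 falls outside the window). Total 6 + 4 = 10.

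**2. Contacts for an early stopper.** The protocol supports more than one reading:

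| Reading | Stops after week 2 | Stops after week 4 |
|---|---|---|
| Only the early-discontinuation list applies | weeks 1, 2, 6, 8, 10 = 5 | weeks 1–4, 6, 8, 10 = 7 |
| Weekly calls also continue | 10 | 10 |
| Leaves assessment for a new treatment | 2, plus the early week 10 set | 4, plus the early week 10 set |

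**3. What a total can hide (illustration).** Assume arms of 6 and 5: 11 randomised, from a block of 12 split 6:6. Assume also that each repeat report is entered as a new event. In arm A, one participant reports one symptom at all 10 contacts and five report nothing. In arm B, each of five participants has one event.

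- Event totals: A 10, B 5.
- Participants with an event: A 1/6 = 17%, B 5/5 = 100%.

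The ranking reverses. At the planned 12 per arm, the same example needs two such symptoms (20 against 12).

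**4. Chance imbalance with equal true risk (simulation).** Events per participant were drawn with an assumed mean of 3, in 200,000 runs. The dispersion d is also assumed, with variance = mean + d × mean². The table gives the chance that events per participant differ at least 2-fold between arms:

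| Arms | d = 0 (independent) | d = 1 | d = 2 |
|---|---|---|---|
| 6 and 5 | 6% | 35% | 49% |
| 12 and 12 | 0.6% | 16% | 29% |

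When events cluster within people, a 2-fold difference in event rate is unremarkable at this size.

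**5. What a zero allows.** For 0 of n, the exact two-sided 95% upper limit is 1 − 0.025^(1/n).

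- n = 11: 1 − 0.025^(1/11) = 28.5%
- n = 24: 1 − 0.025^(1/24) = 14.2%
- Assumed arms of 6 and 5: 45.9% and 52.2%

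If fewer than 11 meet the SAP's definition of the analysis population, the limit rises. For n = 10 it is 30.8%.

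**The case against.** The strongest defence is that this is a small descriptive pilot and that the promised AE tables may well show participants. They may, but nothing commits to it, and the one estimate that is defined counts events.

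A reader might infer that a lasting symptom will be counted ten times, so that one participant outweighs a whole arm. The documents do not support that. They say side effects are asked about at each contact, not that each answer is a new adverse event. Even if repeats were counted, at the assumed mean of 3 events per participant an arm of 5 or 6 would total about 15 to 18, more than one symptom counted ten times. Step 3 is a possibility, not a forecast.

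A reader might also infer that early stoppers have only five contacts, so that a more toxic arm would look safer. That is one reading; the Treatment Phase text can be read as keeping the weekly calls. Drop-out by schedule is also examined under secondary aim 3, so an excess of stopping would be visible there. What stands is that follow-up after stopping may be thinner, and that it ends for those who start a new treatment.

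Nor do the documents support any specific variance inflation for the event count. They give no within-person correlation, and the SAP plans no test or interval on the count.

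Two further objections are fair. Zero participants with any event is implausible, given the reported stopping for adverse events; the limits in step 5 matter for serious or specific events. And with overlapping background symptoms, a crude proportion with any event could approach 100% in both arms, so the replacement needs a baseline rule.

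**Conclusion.** The point holds as a defect in a stated method, and it should be corrected. The number of adverse events per group does not show how many participants were harmed. With 11 participants it can be driven by one or two people, and it comes without an interval. The absence of a participant-level estimate, an interval and a repeat-report rule follows directly from the SAP text, and the 10 contacts from the protocol's schedule. The limits of 28.5% (0/11) and 14.2% (0/24) need only the sample size.

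The size of any distortion between arms is not established. It depends on how repeat reports are entered, on which follow-up reading applied to early stoppers, and on assumed event rates and clustering. Even perfectly merged events would still lack a participant denominator and an interval.

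**What to change.** Replace the second sentence of the primary aim 1 analysis with participant-level estimates:

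- **Estimate:** number and percent of participants with at least one event that is new or worse than baseline, overall and by symptom, by worst severity where graded, with exact 95% confidence intervals.
- **Groups:** by randomised arm (8-week and 4-week), in place of the active and sham labels, since both arms receive disulfiram. Also pooled over both arms for weeks 1–4, when the planned schedule is the same.
- **Event counts:** secondary only, with a stated rule for merging repeat reports and with observation time per arm.
- **Tables:** state the unit of the SAE and AE tables, and state whether weekly calls continued after early stopping.

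This needs no new visits. It costs SAP wording and some extra analysis, and the intervals will be wide. Before finalising, confirm that baseline symptoms, onset and end dates, and severity grades were recorded; the documents do not confirm this. Where they were not, report by symptom without severity or episode merging, and say so. If unblinding has already taken place, label the change as made afterwards.

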There are some risks associated with travel during the COVID-19 pandemic for participants completing study procedures remotely or via the hybrid protocol. The number of laboratory assessments and in-person assessments has been reduced to minimize risk. Nonetheless, for safety-related reasons, it will still be necessary for participants to attend some assessments in-person.

Describe procedures for minimizing risks

Treatment with Disulfiram

1. Disulfiram-alcohol reaction. Patients are required to be alcohol-free during this study and for at least 2 weeks prior to starting the study and for 6 weeks after receiving the last dose of study medication (I.e from weeks 8-14). The consent form will describe this reaction so that patients will be aware of the typical symptom profile should he/she inadvertently consume an alcohol-containing product; this will also be described in detail to the patient by the study clinician. Patients will also be advised to check labels of all consumed products to ensure there is no alcohol within the food preparation (e.g., sauces, vinegar, cough medication).

2. Patients will be monitored for side-effects of the medication during the clinic visits and weekly phone check-ups. The number of pills taken (either 2 or 1 or none) each day can be adjusted based on tolerability

and clinician's judgment. Intolerable side effects or clinically severe worsening that is sustained for 2 consecutive assessments will result in withdrawal from the study.

3. To reduce the risk of rare but serious adverse effects, patients will be excluded from enrollment in the study if there is:

- a. Liver: evidence or history of liver disease or insufficiency
- b. Psychiatric: a lifetime history of psychosis or of bipolar disorder or recent or current suicidality
- c. Substance use: alcohol or substance abuse disorder within the past 2 years
- d. Neurologic: a lifetime history of seizures or history of abnormal EEG
- e. Cardiac: a current or lifetime history of coronary artery disease or heart failure.

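### The only by-group adverse event count stops at week 10, although safety enquiry runs to week 12 and follow-up to week 14, and the SAP does not say which period its adverse event tables cover

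*Combined protocol and SAP*

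**What the plan says.** The SAP row for the primary aim 1 analysis has two parts.

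- The first part has no time limit: "Tables on all mortality rate, SAE and AE will be generated".
- The second part is the only safety output that the SAP describes by treatment group, and it has a limit: "number of adverse events in active and sham treatment groups by the end of 10-week period will be computed and reported".

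The SAP row that defines primary aim 1 sets no time limit on the data: "This will be assessed by SAFTEE (systematically) as well as recording all unanticipated adverse events/serious adverse events".

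The protocol continues to observe safety after week 10.

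- Study Procedures lists clinician calls: "Phone-calls at end of Weeks 3, 5,7, 9 and 12 (10-20 mins". Their topics include "If the participant is experiencing side-effects related to disulfiram" and "If the participant has used any kind of substance like alcohol, cannabis etc".
- The Treatment Phase text has all participants seen, in clinic or by telehealth, for follow-up at week 14.
- Criteria for Early Discontinuation says participants are monitored for "side-effects of the medications (Saftee) during the clinic visits or telehealth visits and weekly phone check-ups".
- The section on minimizing risks requires participants to avoid alcohol "for 6 weeks after receiving the last dose of study medication (I.e from weeks 8-14".

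The documents give no reason for ending the safety count at week 10. In the SAP, week 10 is the primary endpoint evaluation.

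**The concern.** Safety is one of the two primary aims, and the study is meant to inform which treatment schedule to take forward. The one group comparison of adverse events planned for that aim closes four weeks before follow-up ends, and it closes inside the period in which the protocol still guards against a disulfiram-alcohol reaction. An event reported at the week-12 call, or at week 14, would be recorded but would not enter the comparison.

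The cut-off also falls unevenly relative to exposure. The 8-week arm finishes disulfiram about week 8, while the 4-week arm finishes about week 4 and then takes placebo. A stop at week 10 leaves the longer arm much less post-drug observation inside the count. The labels active and sham make the line harder to apply, because both arms receive disulfiram.

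**Working it through.** The documents give no event rate, alpha or power for the safety aim, so the check is of the timeline.

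**Inputs**
- Pills end at week 8, the primary evaluation is 2 weeks later, and the last follow-up is 4 weeks after that (SAP, Study Design).
- The count ends at week 10 (SAP, Primary aim#1 analysis).
- The alcohol-avoidance window after the last dose of study medication is 6 weeks, given as weeks 8-14 (protocol, procedures for minimizing risks).
- The last active dose is at about week 8 in the 8-week arm and about week 4 in the 4-week arm, which then has 4 weeks of placebo (SAP, Study Design).
- The sample size was 24 planned and 11 at termination (SAP, Sample size).

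**The plan's own figures**
- Study length: 8 + 2 + 4 = 14 weeks, as stated.
- Alcohol window: 14 - 8 = 6 weeks, as stated.

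**What the cut-off leaves out**
- Share of the study: (14 - 10) / 14 = 4/14 = 29%.
- Share of the alcohol window: (14 - 10) / (14 - 8) = 4/6 = 67%.
- Patient-weeks, assuming full follow-up: 11 × 4 = 44 of 154, or 24 × 4 = 96 of 336.

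**By arm, measured from the last active dose**

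| | 8-week arm | 4-week arm |
|---|---|---|
| Last active dose (about) | week 8 | week 4 |
| Post-drug weeks counted to week 10 | 10 - 8 = 2 | 10 - 4 = 6 |
| Post-drug weeks counted to week 14 | 14 - 8 = 6 | 14 - 4 = 10 |
| Weeks of a 6-week post-drug window lost at week 10 | 4 | 0 |

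The last line applies the protocol's 6-week window to active drug. The protocol itself states the window from the last dose of study medication, which in the 4-week arm is placebo.

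**How likely an omission is**

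Assume that each participant independently has probability p of an event after week 10. The chance that at least one participant's event is left out of the count is 1 - (1 - p)^n. The values of p are assumptions.

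| p | n = 11 | n = 24 |
|---|---|---|
| 2% | 20% | 38% |
| 5% | 43% | 71% |
| 10% | 69% | 92% |
| 20% | 91% | 99.5% |

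For example, with p = 5% and n = 11: 1 - 0.95^11 = 43%.

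**The case against.** The strongest defence has four parts.

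1. **Late events are not discarded.** A reader might infer that anything after week 10 disappears from primary aim 1. The documents do not support that. The sentence before the count promises mortality, SAE and AE tables with no cut-off, and the aim covers all unanticipated adverse events and SAEs. This stands. What remains is that the sentence gives neither the period covered nor a breakdown by arm, so it does not bring late events back into the comparison.

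2. **Bias towards the longer regimen is not shown.** Counting to week 10 gives both arms the same planned time from the start of treatment, and the longer arm contributes about twice the weeks on drug. The gap in time off drug is 4 weeks at week 10 (2 against 6) and still 4 weeks at week 14 (6 against 10), so extending the count does not remove it. This stands: under-counting in the longer arm is a possibility that depends on late events occurring. A reader might also carry the cut-off over to secondary goal 3, the side effect profile by schedule. That goal has no week-10 limit and no analysis row of its own.

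3. **Week 10 is the last well-measured safety point.** Scheduled blood counts and liver tests end at week 10 in the in-person, remote and hybrid schedules, and the neuropathy scales end at week 8 or 10. Use of SAFTEE at week 14 is an inference from the general monitoring statement, because the visit checklist is not in the text available. This stands, and it is why the week-10 figure must be kept. It does not justify leaving out what the week-12 call explicitly asks about.

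4. **The effect on reported proportions is unknown.** One might split 11 participants into 5 and 6 and say that one omitted participant moves an arm by 17 to 20 points (1/6 and 1/5). The documents give no split by arm, and the SAP promises a number of events, not a proportion of participants. That figure should not be used.

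**Conclusion.** The point holds for the between-group count. That count leaves out 4 of 14 study weeks and 4 of the 6 weeks of the protocol's own alcohol window, without a stated reason, while side effects and alcohol use are asked about at week 12 and participants are seen at week 14. The tables promised in the same row may cover those weeks, but the SAP does not say so.

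The uneven reach by arm (2 against 6 weeks after the last active dose) rests on two assumptions: that the two groups to be compared are the 8-week and 4-week arms, and that active dosing ends at about weeks 8 and 4. It means that late events could be under-counted mainly in the longer arm. It does not establish that the planned safety comparison favours that arm, because the documents give no late-event rate.

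The change is worth making: safety is a primary aim, the sample is small enough for a single event to matter, and the correction is a matter of wording and layout.

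**What to change.** Amend the primary aim 1 analysis row as follows.

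- Run the adverse event count by arm through the week-14 follow-up.
- Keep the count to week 10 as a subtotal, identified as the period that ends with the last scheduled blood tests.
- Show events with onset after week 10 on a separate line by arm.
- State that the mortality, SAE and AE tables cover baseline to week 14.
- Name the groups as the 8-week and 4-week arms in place of active and sham.

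The cost is a few words in one SAP row and additional lines in one table. Unblinding already waits until all participants finish follow-up, and analysis follows unblinding, so nothing is delayed. No dose, visit or clinical rule changes.

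The one downside is that ascertainment after week 10 is lighter: a call at week 12 and follow-up at week 14, with no scheduled blood tests. The week-10 subtotal keeps this visible, and a table footnote should say it.
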